This proposed intervention will not directly deprescribe medications; we will not be randomizing patients to medication discontinuation. Instead, we are testing an intervention to prompt consideration of a clinical decision, analogous to a clinical reminder in the electronic health record prompting the provider to consider appropriate care. We propose an innovative approach to promote medication use review that starts by contacting the patient, not the clinician, yet the ultimate decision remains with the patient-provider dyad.

Study Aim

The study primary aim is to examine the impact of a patient-centered intervention to change provider prescribing (the primary outcome), as determined by the frequency with which medications are either deprescribed or de-escalated. Our primary outcome will be the composite of deprescribing and de-escalation of target medications, identified in pharmacy dispensing records of the Corporate Data Warehouse (CDW).

Hypothesis

The hypothesis is deprescribing will be greater for Veterans receiving the intervention brochure than for those in the historical control group.

Study sites

We will target Veterans at three primary care sites who meet eligibility criteria and are prescribed the target medication at the time of their scheduled primary care visit (in-person, video technology-based, or telephone clinics). These sites were selected based upon ability to recruit adequate samples, geographic variability, and patient population. We will include all PCPs at VA Medical Centers (VAMCs) and Community Based Outpatient Clinics (CBOCs), except for resident clinicians, as these trainees are likely to turn over during the intervention.

Randomization

Previous research, including our pilot study, revealed differences in deprescribing tendencies across providers. Thus, although our intervention intends to engage patients, our study design prioritizes comparisons of patients within the same provider to maximize power. At each intervention site, individual PCPs will be randomized to the sequence of medication cohorts. We will randomize PCPs to one of the three medication groups at the beginning of the first (month 1) and second (month 7) window and assigned them to their

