remaining medication group at the start of the third (month 13) window. Our primary comparisons are between “brochure-intervention” patients and “baseline” patients (matched in terms of eligibility) from the same provider. Each patient will only have one opportunity to receive a brochure, even if they subsequently meet eligibility criteria for receipt of a second, different brochure. This allows equal exposure to the intervention for all Veterans since the impact of a second brochure might be influenced by the first brochure.

Although our primary comparison is between patients of the same provider pre- and post-intervention, we will also collect data at non-equivalent control sites matched by geography who will not receive the intervention; all data on control patients will be from the Corporate Data Warehouse (CDW). Including additional control sites will allow us to address potential temporal trends in deprescribing over the timeframe of our study that are not due to our intervention. The use of separate control sites (rather than randomizing some PCPs at each intervention site to control conditions) was preferred due to concerns about potential contamination across intervention and control conditions within sites. For both the control sites and the pre-intervention baseline period, we will identify patients who would have been eligible for the study; patients meeting criteria for multiple cohorts will be randomly allocated to only one.

Study Cohorts

The intervention cohort will consist of eligible patients in one of the three medication groups with an upcoming PCP appointment during the study enrollment period. We will create a comparison historical control cohorts comprising eligible patients in each medication group who were seen by the same PCPs at the same sites as our intervention cohort eighteen months to one year before our intervention cohort window to allow for comparable follow-up time before the intervention commenced. Patients in the intervention cohorts will be excluded from the historical control cohorts.

Medication Groups

To be enrolled in the study intervention or control cohort, patients needed to meet eligibility criteria for one of three medication-based groups. We have selected three medication-based patient groups based upon variations in 1) type of potentially inappropriate use, 2) medication factors (potential benefit and harms of continued use), and 3) anticipated interest in deprescribing by patients and providers.

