We will query CDW for 6 months following the date of each scheduled primary care visit to assess our primary outcome of deprescribing. Based upon findings in our pilot study, medication orders may not be discontinued in electronic health records even if discussions occur in the clinic visit (e.g., the PCP tells the patient to deprescribe but does not change the order). Notably, because our primary objective is to improve safe prescribing and reduce PIMs, pharmacy dispensing data best reflects our deprescribing outcome. As per our definition, either complete cessation or dose reduction will be fulfillment of our primary outcome.

Modeling our approach after the methods of Steinman, Sussman, and Martin, we will use non-refill of the medication in the 6 months following the primary care appointment as our a priori definition of cessation, based upon dispensing dates.^{4,5} Per VA Pharmacy policy, medications are only refilled upon request, and therefore, non-refill of a medication can indicate that it was discontinued, it expired (typically one year after it was ordered), or the patient did not refill it. If the medication continues to be dispensed, we will determine any reduction in the total daily dose, indicating de-escalation (one component of our deprescribing definition). An

exception to the de-escalation rule will be for insulin, where only complete cessation will qualify since dose changes are less likely to be reflected in the order compared to oral medications.

Consistent with our conceptual framework, we will also assess patient and provider factors that may influence deprescribing. Patient factors will be obtained from CDW, and will include age, race, sex, Elixhauser comorbidities in the two years prior to the scheduled primary care visit. Provider factors include sex, discipline, age, and site.

To assess potential ADWEs, we will ascertain if the deprescribed medication is subsequently restarted or returns to original dosing. We will then query CDW for diagnoses of GI bleeding for the PPI cohort, diabetic ketoacidosis or hyperosmolar hyperglycemic state for the DM cohort, and seizure for the gabapentin cohort in the year following the index visit. Note, we consider substitution to a lower potency medication (e.g., histamine-2 receptor antagonist for a PPI) to be a neutral or desirable event and not an ADWE.

Statistical Analysis Plan (see attached statistical analysis plan for greater detail)

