Veterans receiving the intervention (brochure) and survey – Exclusion criteria have been carefully incorporated to help minimize Veteran risk prior to enrollment. Further, as noted, we are not randomizing patients to have medications withdrawn. The primary intervention is distribution of information directly to patients. It is important to note that the decision to deprescribe or not remains in the purview of the patient-provider dyad. We will provide a brief cover letter when sending the medication-specific brochure to patients, and the medication-specific brochure states multiple times to not decrease or discontinue a medication without first consulting with a clinician. We are also mailing the brochures two weeks prior to a primary care visit, so if patients decide they want to stop a medication, they will already have an appointment scheduled. Taken together with the fact that patients and providers already have the ability to make deprescribing decisions, the risk of this study is not greater than current standard practice.

Risk from breach of confidentiality – In order to assure appropriate research subject selection and high-quality data collection, all study personnel will undergo training in the study protocols. We will take all necessary steps to ensure the protection of confidential information in accordance with VA regulations and other applicable laws. All identifiable data will be protected from improper use or disclosure. Only research team members will have access to data. We will enter survey data into an electronic database with a unique identifier, removing any Protected Health Information (PHI). We will store all electronic data entirely within the VA network, which is protected by firewalls. User identification codes limit access to specific directories and files. We will not include names on audio-recordings or transcriptions, and publications will not identify individual participants or the sites from which they were recruited. We will not disclose identifiable information to any other person or entity outside VA, except as required by law, for authorized oversight of this research study, or for approved use in another study by an IRB. We will store physical data in locked cabinets within the Section of General Internal Medicine and Center for Healthcare Organization and Implementation Research (CHOIR) offices at VA Boston

Potential Benefits

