To identify dose reductions, we calculated the total daily dose (TDD) of the target medication as [dose*(quantity/days supplied)].^{1,2} Substitutions within a medication drug class (e.g., pantoprazole to omeprazole) were standardized to one medication within each class. We only compared TDD at 6 months to that at the index visit for oral medications because insulin dose adjustments are not consistently documented within the electronic health record. Combination insulin products were separated into their long acting and short acting components and analyzed separately. We allowed a 10% buffer for days' supply of PPI, sulfonylurea, and gabapentin (e.g., 33 days for a 30-day supply) to account for missed doses and 100% buffer for insulin due to dispensing requirements (e.g., minimum vials dispensed regardless of dose).

Patient factors and provider characteristics (age, gender, profession) were included as covariates in the model. Based on our conceptual model and using data from CDW, patient factors included age, race, sex, and Elixhauser comorbidities in the year prior to the scheduled primary care visit.^{4,5}

Additionally, we planned to examine whether the effectiveness of the brochure intervention was associated with target medication.

Interim & Final Analysis

Our primary comparisons were between “brochure-intervention” patients and “historical control” patients (matched in terms of eligibility) from the same primary care provider. To investigate the impact of the intervention brochure on deprescribing, Hierarchical Generalized Linear Modeling (HGLM) was used to account for the nesting of patients within providers. This approach provided information not just about the average effectiveness of the intervention, but also about how much variation there is in the intervention impact across providers. In all models, Level 1 (patient-level) intercepts and slopes were treated as random effects, and parameters were estimated with robust standard errors. Using this approach of nesting patients within providers at intervention sites, for our primary analysis, we compared the likelihood of deprescribing among patients in the pre-intervention (“historical”) period to that for patients in the intervention periods who were mailed the brochure. We predicted that intervention patients would be significantly more likely to have deprescribing than patients in the pre-intervention period with the same eligibility criteria. We then examined whether the

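### No booking lead time is stated for historical controls, so visits booked at short notice can be control index visits but not brochure index visits

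*Protocol*

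**What the plan says.** **Brochure group.** The Protocol (*Study Cohorts*) takes eligible patients "with an upcoming PCP appointment during the study enrollment period". Under *Procedures to Minimize Risk* it adds: "We are also mailing the brochures two weeks prior to a primary care visit". The SAP (*Interim & Final Analysis*) analyses the intervention-period patients to whom a brochure was mailed.

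**Historical controls.** The Protocol (*Study Cohorts*) defines them as "eligible patients in each medication group who were seen by the same PCPs at the same sites as our intervention cohort", in an earlier window. Under *Randomization* it says of the baseline period and the control sites that "we will identify patients who would have been eligible for the study". Both documents describe the two groups as matched on eligibility.

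**The visit.** *Study sites* describes the target population as Veterans who are eligible and "are prescribed the target medication at the time of their scheduled primary care visit". *Study Measures* starts the outcome clock in the same terms: "We will query CDW for 6 months following the date of each scheduled primary care visit". The SAP (*Endpoints & Covariates*) also dates comorbidities back from the scheduled visit.

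Neither document states a minimum interval between booking and visit for controls, or says which control visit sets the index date.

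**The concern.** The primary analysis is a before-and-after contrast within provider, so it depends on both groups being drawn in the same way. One group is picked prospectively from appointments that leave time for a mailing. The other is picked retrospectively from visits that took place. A patient whose visit was booked three days ahead could not have been mailed a brochure on the stated timetable, but the same patient fits the written definition of a control.

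Short-notice visits may differ from planned ones in ways that bear on the outcome. They may leave less time to review long-term drugs, or they may bring drug changes for other reasons. The first would lower the control rate and favour the brochure. The second would raise it and count against the brochure.

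This is separate from attendance. The difference in booking would remain if every booked patient attended.

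**Working it through.** **1. Do the written rules differ?**

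| | Brochure group | Historical controls |
|---|---|---|
| When identified | Before the visit | After the visit |
| Visit required | Booked, with a mailing about two weeks ahead | Seen by the same provider |
| Booking lead time | About 14 days, implied by the mailing | None stated |

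Eligibility matching does not clearly close this gap. The Protocol's cohort and exclusion criteria cover drug, dose, duration, diagnosis, laboratory values and age; booking is not among them. In *Study Cohorts*, being eligible and having an appointment are stated as two separate conditions.

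**2. Does anything in the analysis correct it?** The SAP's covariates are patient age, race, sex and comorbidities, and provider age, gender and profession. None records visit type or lead time. Nesting within provider does not help, since one provider can see both kinds of visit. The control-site analysis (*Other analytical subsets*) compares periods, not booked visits with short-notice ones.

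**3. The plan's own figure.** Inputs from SAP *Statistical Power*: 1,990 + 894 + 758 = 3,642 brochures, 20% attrition, 20 patients per provider, ICC 0.05, rates 4.21% and 6.55%, two-sided alpha 0.05. Equal group sizes are an assumption, because no control-group size is given.

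- Per group after attrition: 3,642 × 0.80 = 2,913.6
- Design effect: 1 + (20 − 1) × 0.05 = 1.95
- Effective n per group: 2,913.6 / 1.95 = 1,494
- Power for 4.21% against 6.55%: 80.9%, against 80% stated

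The stated power reproduces. The planned difference is 6.55 − 4.21 = 2.34 points.

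**4. Illustrative size.** The documents give neither the short-notice share nor the deprescribing rate at such visits, so both are assumed. Shift in control rate = share × rate difference.

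- Low: 0.10 × 1 point = 0.1 point; 0.1 / 2.34 = 4% of the planned difference
- High: 0.30 × 2 points = 0.6 point; 0.6 / 2.34 = 26%

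**5. Effect on the test.** Let booked visits have a rate of 4.21%, and let a share s of control visits have k times that rate. The control rate is then 4.21 × (1 − s + s·k). Values of 0.5 and 1.5 for k put the short-notice rate 4.21 × 0.5 = 2.1 points below or above the booked rate, about the top of the range in step 4. Effective n stays at 1,494 per group.

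| s | k | Control rate | Spurious difference (brochure minus control) | Two-sided rejection if brochure has no effect | Power if brochure rate is 6.55% |
|---|---|---|---|---|---|
| any | 1 | 4.21% | 0 | 5.0% | 80.9% |
| 10% | 0.5 | 4.00% | +0.21 point | 6.0% | 87.7% |
| 30% | 0.5 | 3.58% | +0.63 point | 14.5% | 96.0% |
| 10% | 1.5 | 4.42% | −0.21 point | 5.9% | 72.5% |
| 30% | 1.5 | 4.84% | −0.63 point | 13.2% | 52.2% |

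With k below 1, the apparent gain in power is bias. With k above 1, a real effect is partly hidden.

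**The case against.** The strongest reply is that the plan already covers the point. Controls must be eligible as well as seen, and the rule that "we will identify patients who would have been eligible for the study" can be read to include having an appointment that would have triggered a mailing. The repeated word scheduled can be read to exclude walk-ins. The two-week figure comes from one descriptive sentence in a risk section; the *Study overview* says only that the brochure comes before a scheduled appointment. The outcome is dispensing over six months in patients with at least 90 days on the drug, so what happens at a single index visit is diluted. The 2.34-point yardstick is also the smallest detectable effect. The SAP thinks 15% reasonable to expect, and against 15 − 4.21 = 10.79 points a shift of 0.1 to 0.6 point is about 1% to 6%.

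Much of this stands. The exposure probably narrows to appointments booked between one and 13 days ahead. Dilution is plausible, and the study team may have applied a lead-time rule without recording it. It does not settle the matter, because a visit booked yesterday is still scheduled, the listed criteria do not mention booking, and the sentence that defines the historical cohort turns on having been seen. An analyst could include short-notice visits without departing from the text.

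A reader might infer that controls needed only to have been seen, or that short-notice visits did enter the control group. The documents support neither: eligibility is part of the control definition, and nothing shows how the retrospective query was built.

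**Conclusion.** The point holds as a difference in the written selection rules: short-notice visits can enter the control group and, if mailing follows the stated timetable, cannot enter the brochure group. Nothing in the planned analysis would correct this.

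A reader might go further and infer that the brochure's effect is overstated. The documents do not support that. If deprescribing is equally frequent at both kinds of visit there is no bias; if it is more frequent at short-notice visits, the bias runs against the brochure. The shift of 0.1 to 0.6 point (4% to 26% of the 2.34-point planned difference) rests wholly on an assumed share of 10% to 30% and an assumed rate difference of 1 to 2 points. The power and rejection figures also assume equal group sizes.

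This is a cheap improvement to the primary comparison. It does not show that the comparison failed.

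**What to change.** In the Protocol, *Study Cohorts*, state that index visits for historical and control-site patients are drawn from primary care appointments already booked at least two weeks before the visit date, **whether or not attended**, using the same query and the same index-visit selection rule as for brochure patients. The attendance clause matters because the SAP expects 20% of mailed patients to miss their visit, so a lead-time filter that kept the condition of having been seen would leave that second difference in place. Any rule for choosing among several visits, such as taking the first, should apply to all groups or to none.

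If the control cohort is already built, as the SAP's past tense suggests, add a sensitivity analysis of the primary model restricted to control appointments booked at least two weeks ahead. If such a rule was applied but not written down, one sentence saying so resolves the point.

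The cost is a change to a retrospective query and somewhat fewer controls. It assumes that the Corporate Data Warehouse holds usable booking dates, which the documents do not say.

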Official Title: Engaging Patients to Promote Deprescribing

NCT Number: NCT04294901

Document Date: November 14, 2019

Statistical Power

Based on fiscal year (FY) 2017 data, we estimated that we would mail brochures to at least 1,990 PPI patients, 894 Diabetes-Hypoglycemia patients, and 758 Gabapentin patients during the study. For apriori statistical power analyses, we made the following assumptions based on our pilot data: an overall baseline deprescribing rate of 4.21%, a conservatively high intraclass correlation coefficient (ICC) of 0.05 (for non-independence among patients of the same provider), an average of 20 eligible patients per PCC or WHC provider, and a 20% attrition rate (i.e., patients who receive the intervention brochure but do not attend their clinic visit). With these assumptions, we determined that we would have 80% power (for two-tailed tests at $\alpha=0.05$) to detect deprescribing rates following the intervention as small as 6.55% overall for these low-end estimates of our projected sample. Moreover, even at these low-end estimates of the projected sample size, we determined we would have 80% power to detect an overall deprescribing rate as low as 15% among the combined intervention cohorts even if the ICC was as high as 0.1, the baseline deprescribing rate was as high as 10%, and/or the attrition rate was as high as 40%. Notably, a deprescribing rate of 15% was reasonable to expect given that we found similar or higher rates in our pilot study.

We conducted analyses using SAS.³

Endpoints & Covariates

The primary hypothesis was deprescribing would be greater for Veterans receiving the intervention brochure than for those in the historical control group.

The primary outcome was binary: deprescribing versus not, assessed via pharmacy dispensing data from the VA Corporate Data Warehouse (CDW). More specifically, six months from the index date, an analyst queried the CDW to determine medication outcomes (e.g., complete deprescribing, dose reduction). We selected 6 months because prescriptions are often filled as a 90-day supply and using a shorter observation window might not fully identify that the prescription was not refilled. We removed patients who died within six months from their index data from intervention and historical controls at the analysis stage to avoid misattributing deprescribing to the intervention rather than death.

To identify dose reductions, we calculated the total daily dose (TDD) of the target medication as [dose*(quantity/days supplied)].^{1,2} Substitutions within a medication drug class (e.g., pantoprazole to omeprazole) were standardized to one medication within each class. We only compared TDD at 6 months to that at the index visit for oral medications because insulin dose adjustments are not consistently documented within the electronic health record. Combination insulin products were separated into their long acting and short acting components and analyzed separately. We allowed a 10% buffer for days' supply of PPI, sulfonylurea, and gabapentin (e.g., 33 days for a 30-day supply) to account for missed doses and 100% buffer for insulin due to dispensing requirements (e.g., minimum vials dispensed regardless of dose).

Patient factors and provider characteristics (age, gender, profession) were included as covariates in the model. Based on our conceptual model and using data from CDW, patient factors included age, race, sex, and Elixhauser comorbidities in the year prior to the scheduled primary care visit.^{4,5}

Additionally, we planned to examine whether the effectiveness of the brochure intervention was associated with target medication.

Interim & Final Analysis

Our primary comparisons were between “brochure-intervention” patients and “historical control” patients (matched in terms of eligibility) from the same primary care provider. To investigate the impact of the intervention brochure on deprescribing, Hierarchical Generalized Linear Modeling (HGLM) was used to account for the nesting of patients within providers. This approach provided information not just about the average effectiveness of the intervention, but also about how much variation there is in the intervention impact across providers. In all models, Level 1 (patient-level) intercepts and slopes were treated as random effects, and parameters were estimated with robust standard errors. Using this approach of nesting patients within providers at intervention sites, for our primary analysis, we compared the likelihood of deprescribing among patients in the pre-intervention (“historical”) period to that for patients in the intervention periods who were mailed the brochure. We predicted that intervention patients would be significantly more likely to have deprescribing than patients in the pre-intervention period with the same eligibility criteria. We then examined whether the

intervention effectiveness was moderated by the target medication. We did not expect a discontinuation rate of 100%, as patients may have an indication to remain on the medication. No adjustments were made to p-values or confidence intervals for multiple comparisons for the primary outcome.

No interim analyses were planned.

Missing Data

We examined the incidence of missing data by medication cohort (PPI vs. DM vs. Gaba). We expected very low rates of missing data, given that our primary analyses rely on CDW data. For missing data, we implemented a series of sensitivity analyses using imputation (coding as “missing” for categorical variables and imputed means for continuous variables) to assess the degree of bias that might be induced by missing data. The results did not change in direction or significance.

Methods for dealing with data transformations

We did not apply any data transformations. All data underwent standard preliminary visualization and quality screening to test for potential violations of assumptions (e.g., distributional assumptions regarding normality, homogeneity of variance, linear relationships, outliers, ceiling/floor effects).

Other analytical subsets

The intervention is designed to target and engage patients, but it is possible that the intervention may be more effective with certain providers. Therefore, a null hierarchical model was used to estimate intraclass correlations to characterize the percent variance explained at the patient, provider, and site levels.

We used HGLM to examine whether the likelihood of deprescribing changes over time at our control sites (instead of from the pre-intervention period) to rule out alternative explanations for the effect of our intervention that rely on temporal trends in deprescribing unrelated to our intervention (e.g., other deprescribing initiatives). We elected not to include temporal deprescribing trends in the manuscript since there was no evidence of significant temporal trends.

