1. Proton Pump Inhibitor Cohort (PPI)

The PPI cohort will be defined as patients with prescriptions for any PPI at any dose for 90 consecutive days in patients of any age.

2. Diabetes – Hypoglycemia Risk (DM-HR)

To create diabetes cohorts, we identify overly-controlled patients with diabetes based upon International Classification of Diseases, Tenth Revision, Clinical Modification (ICD-10-CM) diagnosis codes, most recent HbA1c <7%, as well as one or more of the following criteria: 1) age 65 or older, 2) renal insufficiency defined as creatinine >2 mg/dL, or 3) cognitive impairment defined by a diagnosis of cognitive impairment and/or prescription for an acetylcholinesterase inhibitor (e.g., donepezil). Patients in the DM-HR group needed to have a current prescription for either insulin or sulfonylurea with at least 90 consecutive days on the medication in the prior year.

3. Gabapentin (Gaba)

The gabapentin cohort will include patients prescribed a total daily dose of gabapentin >1800mg for a minimum of 90 days.

Subject Exclusion Criteria

We will not exclude women or minorities, but children will not be eligible for participation.

1. Proton Pump Inhibitor Cohort (PPI)

In response to feedback from our pilot study, we will exclude diagnoses for which PPI continuation would be appropriate (e.g., Barrett’s esophagus, or those prescribed chronic glucocorticoids or NSAIDs).

2. Diabetes – Hypoglycemia Risk (DM-HR)

No exclusion criteria.

3. Gabapentin Cohort (Gaba)

We will exclude patients with recommended indications for gabapentin, including documented neuropathic pain using established criteria, those with seizure disorders, documented neuropathic pain, and cancer-related pain.

Recruitment

As we did for our IRB approved pilot study, we are requesting a waiver of informed consent and a waiver of HIPAA authorization to identify eligible Veterans to whom we will mail brochures.

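### In the diabetes (DM-HR) cohort only within-class substitutions are neutralised, so a sulfonylurea stopped or reduced while insulin is newly started can be counted as deprescribing

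*SAP*

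**What the plan says.** **Cohort.** Protocol, Medication Groups: "Patients in the DM-HR group needed to have a current prescription for either insulin or sulfonylurea". The PPI cohort is one drug class and the gabapentin cohort one drug.

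**Success.** Protocol, Study Measures, defines cessation as no refill of the medication in the six months after the appointment. If dispensing continues, a lower total daily dose also counts. Insulin is an exception: nothing short of complete cessation counts. For DM-HR, neither document says whether the medication means the agent, the class, or any insulin or sulfonylurea.

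**Substitution.** SAP, Endpoints & Covariates: "Substitutions within a medication drug class (e.g., pantoprazole to omeprazole) were standardized to one medication within each class". The sentence stands in the paragraph on dose reductions. The protocol's only remark on changing to a different class concerns lower-potency replacements. It says they are not adverse drug withdrawal events and does not define the primary outcome.

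**Combination insulin.** The same SAP paragraph says these products were "separated into their long acting and short acting components and analyzed separately". No rule turns two component results into one patient result, although both documents make the primary outcome binary.

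**Moderation.** Both documents plan to test whether the brochure's effect differs by target medication, so DM-HR is compared with the other cohorts.

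**The concern.** The outcome follows a target medication, and the only protection against counting a switch as a stop works inside one class. That protection is incomplete where the cohort spans two classes. A patient who leaves a sulfonylurea for insulin meets the literal cessation definition, and one whose sulfonylurea dose falls as insulin is added meets the dose-reduction definition. Both remain on a drug that qualifies for the cohort, and no rule stops either from counting as a success.

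The combination-insulin wording raises a related question: is losing one component while the other continues a success, a non-event, or undefined?

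At stake are events that are not reductions in hypoglycaemia-risk treatment. At a low base rate these dilute the main contrast, and they could make DM-HR look different from the other cohorts because of coding. Equal switching in the two periods is also not guaranteed: the brochure discusses alternative medicines, and the controls come from an earlier calendar period.

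**Working it through.** **Inputs (SAP, Statistical Power)**
- Projected brochures: "at least 1,990 PPI patients, 894 Diabetes-Hypoglycemia patients, and 758 Gabapentin patients". Total 1,990 + 894 + 758 = 3,642. DM-HR share 894 / 3,642 = 24.5%.
- Baseline: "an overall baseline deprescribing rate of 4.21"%.
- Target: 80% power, two-sided 0.05, to "detect deprescribing rates following the intervention as small as 6.55% overall". Difference 6.55 − 4.21 = 2.34 points.
- Clustering: "a conservatively high intraclass correlation coefficient (ICC) of 0.05" and "an average of 20 eligible patients per PCC or WHC provider". Design effect 1 + 19 × 0.05 = 1.95.
- Attrition 20%.
- Allocation is not stated; 1:1 is assumed.

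**Step 1: reproduce the plan's figure.** Effective n per group = 0.8 × 3,642 / 1.95 = 1,494. With the pooled-variance comparison of two proportions,

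power = Φ{[Δ√n − 1.96 √(2p̄(1−p̄))] / √(p₁q₁ + p₂q₂)},

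p₁ = 0.0421 and p₂ = 0.0655 give 81.0%. The rate detectable at 80% power is 6.52%, against 6.55% stated. The required size is 1,459 × 1.95 / 0.8 = 3,556 per group, against 3,642. This is close enough to use as a base. It is not the only route: taking 3,642 as both groups together, with 20% attrition and no design effect, also gives 6.55%.

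**Step 2: overall effect of switches counted as successes.** Let s be the share of DM-HR patients so counted, equal in both periods. The documents give no s; 0.5% to 5% is an assumption. Each period's overall rate rises by 0.2455 × s. The 2.34-point difference is unchanged, but variance rises and the ratio shrinks.

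| s | Points added overall | As share of 2.34 | Power | Rate ratio |
|---|---|---|---|---|
| 0 | 0 | 0 | 81.0% | 1.56 |
| 0.5% | 0.12 | 5% | 80.1% | 1.54 |
| 1% | 0.25 | 10% | 79.3% | 1.53 |
| 2% | 0.49 | 21% | 77.7% | 1.50 |
| 5% | 1.23 | 52% | 73.1% | 1.43 |

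**Step 3: effect within DM-HR.** Here s is added in full. No DM-HR rate is given, so the overall rates are borrowed as an assumption:
- s = 0: 6.55 / 4.21 = 1.56
- s = 1%: 7.55 / 5.21 = 1.45
- s = 2%: 8.55 / 6.21 = 1.38
- s = 5%: 11.55 / 9.21 = 1.25

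**Step 4: could switching alone create the effect?** To produce the whole 2.34 points, DM-HR switching would have to differ between periods by 2.34 / 0.2455 = 9.5 points.

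**Step 5: the insulin rules side by side.** The protocol requires complete cessation but does not say whether of all insulin or of one product. The SAP separates components but does not say how they recombine. If insulin is one class, the within-class rule would absorb a change between components, which pulls against analysing them separately. The text does not settle which reading applies.

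**The case against.** The strongest reply is that this is an undefined term, not documented miscounting. Nothing says a switch to insulin was scored as success, and the substitution sentence belongs to the dose calculation. That stands, and is why the point says such a patient can be counted. But the gap is in the primary outcome, and the literal reading favours success.

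The cohort also makes the scenario less likely. Patients must have a most recent HbA1c below 7% plus a risk criterion, so starting insulin within six months may be uncommon. Only those on a sulfonylurea and not on insulin at index can make this switch, and their share is not given. This limits the size, not the gap.

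Three stronger readings are tempting, and the documents do not support them.
- **A large share of DM-HR events is false.** One per cent of 894 is about 9 patients, and 894 × 4.21% is about 38 events, which suggests 24%. But 4.21% is the overall rate, and no switch rate is given. At the 15% that the SAP calls reasonable to expect after the intervention, 9 would be 7% of 134. If 4.21% was measured under the same definition, it may already include switches.
- **Stopping one insulin component counts, or one patient yields two results.** The protocol's complete-cessation rule may mean all insulin, the split may be mere data handling, and stopping a component may be a real reduction. This is an ambiguity to resolve.
- **DM-HR cessation must mean neither drug is dispensed.** That would remove a patient on both drugs who stops the sulfonylurea and stays on insulin. The protocol does not exclude such patients, and its aim treats stopping a target medication as deprescribing. Redefinition at cohort level is therefore a trade-off, not a correction.

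**Conclusion.** The concern holds in a narrow form. For DM-HR the outcome rules leave cross-class switches unclassified, and a sulfonylurea stopped or reduced with insulin newly started can be counted as success. How combination-insulin components form one patient-level result is unresolved between protocol and SAP.

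If switching is equal in both periods, the consequence is dilution, not a false positive. Overall power falls from 81.0% to 79.3% at an assumed 1%, and to 73.1% at 5%. The DM-HR ratio is affected more: 1.56 falls to 1.45 at 1%. These figures rest on 1:1 allocation, the SAP's design assumptions, the overall rates applied to DM-HR, and an assumed switch rate. Unequal switching could bias the contrast in either direction. The documents do not show that it occurred, and it would have to be very large to explain the whole detectable difference. The point is worth correcting because it concerns the primary outcome and costs little.

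**What to change.** 1. Define the DM-HR target medication in the SAP. State that sulfonylurea cessation or dose reduction does not count as deprescribing when insulin not in use at the index visit is newly dispensed during the six-month window.
2. Leave unchanged the classification of patients on both drugs at index who stop one.
3. Reconcile the protocol's insulin rule with the SAP's component rule, and state how components combine into one result per patient.
4. Apply the same rules to intervention and historical-control patients.
5. Report a sensitivity analysis that counts all cross-class switches, in either direction, and all single-component insulin stops as not deprescribed. Give the number of such patients by period, which would replace the assumed range above.

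The SAP is written in the past tense. If the analysis has been run, state which rule the code applied and show the results under both.

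The cost is a few sentences and a small recode of dispensing data already held, with slightly fewer DM-HR events. This concerns outcome classification only and implies nothing about how patients should be treated.
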